#### Feasibility/Acceptability Outcomes

6. Client Satisfaction Questionnaire-8 (CSQ-8) parent report at post-treatment (total scores) will be compared across groups (BPT vs. CET) using independent samples T-test.

7. Barriers to Treatment Participation Scale (BTPS) parent report at post-treatment (total scores and all subscales). Independent samples t-tests. The Relevance of Treatment subscale will be interpreted as evidence of intervention expectancies.

8. CET only: System Usability Scale (SUS). Child reported feasibility of CET system. Expected to be high (mean of at least 3.5 on 5-point Likert scale, where higher scores indicate better usability). Descriptive statistics only.

9. CET training duration. Total minutes trained and total training games completed will be reported. Descriptive statistics only.

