7. Barriers to Treatment Participation Scale (BTPS) parent report at post-treatment (total scores and all subscales). No significant differences are expected. The Relevance of Treatment subscale will be interpreted as evidence of intervention expectancies.
8. CET only: System Usability Scale (SUS). Child reported feasibility of CET system. Expected to be high (mean of at least 3.5 on 5-point Likert scale, where higher scores indicate better usability).
9. CET training duration. Total minutes trained and total training games completed will be reported. Descriptive; no hypotheses are offered.

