## Sample size

*Describe the sample size of your study. How many units will be analyzed in the study? This could be the number of people, birds, classrooms, plots, interactions, or countries included. If the units are not individuals, then describe the size requirements for each unit. If you are using a clustered or multilevel design, how many units are you collecting at each level of the analysis?*

The final analyzed sample size is expected to be BPT = 27, CET = 27. BPT collection is complete; the last CET group is anticipated to be complete in May/June 2017.

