#### Feasibility/Acceptability Outcomes

Client Satisfaction Questionnaire (CSQ-8; Nguyen et al., 1983). The CSQ-8 is an extensively studied, 8-item generic measure of clients' perceptions of the value of services received. Parents completed the CSQ-8 at post-treatment. Total scores will be used.

Barriers to Treatment Participation Scale (BTPS; Kazdin et al., 1997). The BTPS is a 44-item measure of perceived treatment barriers; item scores are summed to provide a Total Barriers score and 4 subscores: (1) Stressors/obstacles; (2) Treatment demands/issues; (3) Perceived relevance; and (4) Relationship with the Therapist. Parents completed the BTPS at post-treatment. Total scores will be used for each subscale.

System Usability Scale (SUS; Canon-Bowers & Bowers, 2010). The SUS is a 10-item, IRT-developed scale assessing ease of use on a 5-point Likert scale. Children in the CET group completed the SUS each week for a different training game, and at post-treatment for the CET system overall. Total scores will be used.

CET Training Duration. The CET software records training duration for each completed training task; total minutes trained and total completed games are reported.

no file selected

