## Inference criteria

*What criteria will you use to make inferences? Please describe the information you'll use (e.g. specify the p-values, Bayes factors, specific model fit indices), as well as cut-off criterion, where appropriate. Will you be using one or two tailed tests for each of your analyses? If you are comparing multiple conditions or testing multiple hypotheses, will you account for this?*

P-values and Bayes Factors will be reported. P-values will be considered primary in cases of discrepant results (to follow current conventions in the field). P =.05 or lower and BF =3 or greater will indicate significant effects.

For the Bayes Factors, BF10 or BF01 will be reported based on which value is greater than 1 as recommended.

Post-hoc tests will be corrected using Bonferroni corrections for multiple comparisons. No corrections will be made for the omnibus tests. These omnibus tests already include 2 variables per outcome to minimize the number of tests.

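### The only expectancy measure in the plan is a barriers subscale completed after treatment, which cannot isolate what parents expected beforehand

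*Combined protocol and SAP*

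**What the plan says.** Item 7 appears twice, once among the hypotheses (Secondary Outcomes) and once in the Analysis Plan (Feasibility/Acceptability Outcomes). Both versions carry the sentence "The Relevance of Treatment subscale will be interpreted as evidence of intervention expectancies".

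- **Test.** The analysis is given as "parent report at post-treatment (total scores and all subscales). Independent samples t-tests".
- **Prediction.** For the BTPS total and subscales the hypotheses say "No significant differences are expected". No equivalence margin is given.
- **Instrument and timing.** Under Measures, "The BTPS is a 44-item measure of perceived treatment barriers", and "Parents completed the BTPS at post-treatment". No earlier administration is described.
- **Size and criteria.** "The final analyzed sample size is expected to be BPT = 27, CET = 27". The Inference criteria section says "P =.05 or lower and BF =3 or greater will indicate significant effects". It makes p-values primary where the two disagree and does not say whether tests are one- or two-sided.

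The rest of the plan specifies no expectancy or credibility measure. The list of pre-treatment comparisons and potential covariates (Covariates and Data Handling, item 1) contains none. The CSQ-8 measures satisfaction. The SUS measures usability, in the CET arm only. Telling CET children that they were testing games was a step to lower child expectancies. It is not a measurement and does not concern parents.

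**The concern.** Expectancy, as a rival explanation for a treatment effect, is a belief held before or early in treatment. A parent who answers after treatment has already seen how the child fared, and the answer may be shaped by that. A gap between arms could then be a result of perceived benefit, and the absence of a gap could hide different prior beliefs. The two treatments also ask different things of parents. BPT works through the parent, while CET trains the child and its caregiver component changed during the study. Perceived relevance could therefore differ for reasons of content alone.

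What is at stake is the reading of the parent-rated results. The study has no blinding, families were not randomised, and the hypotheses themselves call the ADHD and oppositional-defiant ratings unblinded. The same informant type supplies both those ratings and the score meant to speak to expectancy, at the same post-treatment stage. Following the sentence as preregistered would put into the report a statement about expectancies that the data cannot support in either direction.

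**Working it through.** The plan states no power, effect size or margin for this comparison, and its sample size rationale gives only recruitment dates. There is no figure to reproduce. The main argument concerns timing; the numbers show what a null could add.

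**1. Timing.** The inference concerns a belief before treatment. The Measures section and item 7 of the Analysis Plan both place the observation at post-treatment. No pre-treatment score is specified to adjust for or compare with.

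**2. What the score can separate.** As an illustration, write the post-treatment score (SD 1) as a × prior expectancy + b × perceived benefit + noise. The expected arm difference is a·ΔE + b·ΔB, where ΔE and ΔB are the arm gaps in expectancy and benefit, in SD. The weights are assumptions. With a = b = 0.5:

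| Expectancy gap ΔE | Benefit gap ΔB | Score gap | Simulated share with p ≤ .05 |
|---|---|---|---|
| 0.5 | 0 | 0.25 | 0.147 |
| 0 | 0.5 | 0.25 | 0.147 |
| 0.5 | −0.5 | 0 | 0.050 |

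(20,000 simulated trials per row, 27 per arm.) The first two rows cannot be told apart. In the third, a real expectancy gap leaves no trace. With weights of 0.3 the shares are 0.083, 0.085 and 0.050; with 0.7 they are 0.243, 0.244 and 0.048. The pattern is the same.

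**3. Power if the subscale were a perfect expectancy measure.** Inputs: n = 27 per arm (Sample size); α = .05 (Inference criteria), two-sided assumed; no covariate adjustment; effect sizes d assumed.

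- Degrees of freedom 27 + 27 − 2 = 52; critical t = 2.007.
- Noncentrality = d × √(n/2) = d × √13.5 = 3.674d.
- d = 0.5: noncentrality 1.837, power 0.438, so a real gap is missed 56% of the time.
- d = 0.3: noncentrality 1.102, power 0.191, missed 81% of the time.
- The gap detectable with 80% power is about 0.78 SD.

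**4. Precision.** The 95% interval half-width is 2.007 × √(2/27) = 2.007 × 0.2722 = 0.546 SD. An observed difference of zero would still be compatible with a gap of about half an SD either way.

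**5. Bayes factors.** The plan names no prior. Assume a Cauchy prior of scale 0.707 on the standardised difference.

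- At 27 per arm the Bayes factor for the null (BF01) peaks at 3.65, when t = 0, against the plan's threshold of 3.
- It reaches 3 only when |t| is below 0.69.
- That happens 12% of the time when the true gap is 0.5 SD and 30% of the time when it is 0.3 SD.

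**The case against.** The strongest reply is that the plan says less than a reader might infer.

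- **A null as proof of matched expectancies.** A reader might infer that a non-significant result will be taken to show equal expectancies. The plan does not say so. It predicts no significant difference for the BTPS scores and separately labels one subscale. Its sentence equating no difference with equivalence (Recommended elements) concerns the post-treatment test covaried for pre-treatment scores. This stands.
- **Ruling out bias.** Nor does the plan claim that the subscale excludes expectancy bias. This also stands.
- **Bayes factors.** They would leave many nulls unsupported: a true 0.5 SD gap would yield BF01 of 3 or more 12% of the time, against a non-significant p-value 56% of the time. This is a real qualification. However, p-values take priority when the two disagree, and no Bayes factor changes when the parent was asked.
- **Outcome dependence is not quantified.** The documents show no subscale items, so how far the score follows outcome is unknown. That is why the point says only that it may do so.
- **Reach.** The sentence governs no model, covariate or decision threshold, and the plan openly calls the parent ratings unblinded. This limits the point to interpretation of secondary outcomes.

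A last tempting inference is that prior expectancy was never measured. The documents do not establish this. The registration template lets authors omit variables outside the confirmatory analyses, and pre-treatment testing was part of a larger battery. One can say only that none is specified in this plan.

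**Conclusion.** The concern holds in a limited form. A score collected only at post-treatment, on a scale of perceived barriers, is preregistered as evidence of expectancies, and neither a difference nor a null on it isolates prior expectancy. This rests on the plan's own timing and on no numerical assumption.

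The arithmetic adds that the predicted null would be weak evidence of similarity even with a perfect measure. That part assumes two-sided testing, 27 analysed per arm, no covariate adjustment and effect sizes chosen for illustration.

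The consequence falls on the parent-rated ADHD and oppositional-defiant outcomes. A reader might extend it to the working-memory primary outcome. The documents give less ground for that, because it is a performance test and actigraphy is instrumented, although no one in the study is blinded. The change is worth making because it alters what the report may conclude; no estimate or test result changes.

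**What to change.** Delete the expectancy sentence from item 7 in both places and replace it with:

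> The Relevance subscale is reported as post-treatment perceived relevance, with the arm difference and 95% CI. It is not used as evidence about pre-treatment expectancies. No pre-treatment expectancy measure is specified in this plan, so expectancy bias in the unblinded parent ratings cannot be excluded.

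Use one name for the subscale throughout; the Measures section and item 7 currently differ.

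This is a wording change. It needs no new data, which matters because BPT collection is complete and CET collection nearly so. The cost is that the report loses its only evidence offered on expectancies.

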#### Recommended elements

10. All hypothesized interactions are expected to look like Figure 1 in Redick (2015). In other words, no pre-treatment group differences, and differential improvements favoring the group hypothesized to improve. Should pre-treatment group differences be observed, differential improvements favoring the group hypothesized to improve would be observed when using post-treatment covaried for pre-treatment analysis (residualized gain scores). No differences in this test indicate equivalence between interventions.

11. P-values and Bayes Factors will be reported. P-values will be considered primary in cases of discrepant results (to follow current conventions in the field). P-values = .05 or lower will be considered significant (after Bonferroni corrections for post-hoc tests). Bayes Factors = 3 or greater will be considered significant.

no file selected

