### Variables

*Please list each research question included in this study.*

1. Is CET a feasible and acceptable intervention for caregivers and their children with ADHD? Is its feasibility and acceptability comparable to the current gold-standard psychosocial treatment for ADHD (BPT)?
2. Does CET improve working memory in children with ADHD, and are these improvements superior to those found for BPT (which is not expected to improve working memory)?
3. Does CET improve ADHD symptoms in children with ADHD, and are these improvements non-inferior to improvements associated with gold-standard BPT?
4. (Fidelity Check) Does BPT improve oppositional-defiant symptoms in children with ADHD, and how does CET compare to BPT for these expected improvements?

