## Secondary Outcomes

2. Far-transfer subjective ADHD symptoms: BPT and CET will both show significant reductions in ADHD symptoms measured by unblinded parent ratings. Two scales are used: the norm-referenced BASC-2 (T-scores based on age and gender norms) and CSI-IV (raw symptom severity scores). Both have separate Attention Problems and Hyperactivity/Impulsivity subscales. Both will be tested via 2 group x 2 subscale x 2 time point mixed-model ANOVA. Critical test is the group x time interaction for both. Post-hoc plan follows #1 above.
3. Far-transfer objective (proximal) ADHD symptoms: CET will show greater reductions in actigraph-measured hyperactivity than BPT during the Rapport PH and VS working memory tests. Same 2 group x 2 task (PH-actigraphy, VS-actigraphy) x 2 time points approach as above; same post-hoc plan. Critical test is the group x time interaction. Actigraph data will be PIM intensity scores, summed across 3 actigraphs (non-dominant wrist, left ankle, right ankle).
4. Far-transfer objective (distal) ADHD symptoms: CET will show greater reductions in actigraph-measured hyperactivity than BPT during the low cognitive load Painting tasks at the beginning and end of each testing session. Same 2 group x 2 task (PaintBeginning-actigraphy, PaintEnd-actigraphy) x 2 time points approach as above; same post-hoc plan. Critical test is the group x time interaction. Actigraph data will be PIM intensity scores, summed across 3 actigraphs (non-dominant wrist, left ankle, right ankle).
5. Far-transfer subjective oppositional-defiant symptoms: BPT will show greater improvements in unblinded parent reports of oppositional defiant symptoms on the CSI-IV. Only the ADHD and ODD sections of the CSI-IV were administered. Analysis will be 2 group x 2 timepoints mixed-model ANOVA. Critical test is the group x time interaction. CSI-IV raw symptom scores for the ODD dimension will be used as dependent variable. Bonferroni-corrected paired-sample t-tests for each group separately (pre vs. post), and between-group at post covaried for pre-treatment ODD symptoms are tested because of compelling evidence that BPT improves these symptoms (manipulation check; if no significant reductions in BPT group, may indicate limited BPT efficacy).
6. Client Satisfaction Questionnaire-8 (CSQ-8) parent report at post-treatment (total scores) will be compared across groups (BPT vs. CET). No significant differences expected.

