#### Primary Outcome

1. Near-transfer: 2 group x 2 task x 2 time points (pre, post). Tasks are Rapport phonological (PH) and visuospatial (VS) working memory tests. Critical test is the group x time interaction. The 2 tasks are included in the omnibus ANOVA to (1) address recommendations to probe cognitive abilities using multiple tests, and (2) maximize power for the critical group x time interaction. The 2 working memory tests are considered to tap the same 'central executive' working memory; they differ in whether that central executive is processing phonological or visuospatial information. If the group x time interaction is significant at  $p = .05$  (or lower), it will be followed by Bonferroni-corrected within-group post-hocs for each task and ANCOVA of post-treatment covaried for pre-treatment separately for each task (i.e., residualized gain scores). These post-hocs will also be performed if the main effect of time is significant (but not the group x time interaction) to allow us to better characterize change within each group (i.e., did each treatment produce significant change?). Stimuli correct per trial will be used.

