#### Secondary Outcomes

2. Far-transfer subjective ADHD symptoms: Two scales are used: the norm-referenced BASC-2 (T-scores based on age and gender norms) and CSI-IV (raw symptom severity scores). Both have separate Attention Problems and Hyperactivity/Impulsivity subscales. Both will be tested via 2 group x 2 subscale x 2 time point mixed-model ANOVA. Critical test is the group x time interaction for both. Post-hoc plan follows #1 above.

3. Far-transfer objective (proximal) ADHD symptoms: Same 2 group x 2 task (PH-actigraphy, VS-actigraphy) x 2 time points approach as above; same post-hoc plan. Critical test is the group x time interaction. Actigraph data will be PIM intensity scores collected while the child was completing the PH and VS tests described above. Each data point reflects total hyperactivity score (Rapport et al., 2009), which is computed by summing the PIM activity counts for each of the 3 actigraphs (non-dominant wrist, left ankle, right ankle).

4. Far-transfer objective (distal) ADHD symptoms: Same 2 group x 2 task (PaintBeginning-actigraphy, PaintEnd-actigraphy) x 2 time points approach as above; same post-hoc plan. Critical test is the group x time interaction. Actigraph data will be PIM intensity scores collected while the child was completing the beginning of session and end of session Paint activity (drawing using Microsoft Paint). Each data point reflects total hyperactivity score (Rapport et al., 2009), which is computed by summing the PIM activity counts for each of the 3 actigraphs (non-dominant wrist, left ankle, right ankle).

5. Far-transfer subjective oppositional-defiant symptoms: Included as fidelity check based on evidence that BPT may produce greatest effects on oppositional defiant symptoms. Analysis will be 2 group x 2 timepoints mixed-model ANOVA (only one measure of ODD symptoms was collected). Critical test is the group x time interaction. CSI-IV raw symptom scores for the ODD dimension will be used as dependent variable. Bonferroni-corrected paired-sample t-tests for each group separately (pre vs. post), and between-group at post covaried for pre-treatment ODD symptoms are tested because of compelling evidence that BPT improves these symptoms (manipulation check; if no significant reductions in BPT group, may indicate limited BPT efficacy).

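### Research question 3 asks whether CET is non-inferior to BPT on ADHD symptoms, but the plan tests only for a difference, sets no margin or confidence-interval rule, and elsewhere reads a null result as equivalence

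*Combined protocol and SAP*

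**What the plan says.** The third research question (opening list, under Variables) asks whether CET improves ADHD symptoms and "are these improvements non-inferior to improvements associated with gold-standard BPT".

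The matching hypothesis (Secondary Outcomes, item 2) makes no between-group claim: "BPT and CET will both show significant reductions in ADHD symptoms measured by unblinded parent ratings". The analysis (Analysis Plan, Statistical models, Secondary Outcomes, item 2) is a group by subscale by time mixed-model ANOVA, run once on the BASC-2 and once on the CSI-IV: "Critical test is the group x time interaction for both". Its post-hoc plan is that of item 1: Bonferroni-corrected within-group tests, and an ANCOVA of the post score on the pre score.

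The Recommended elements, in the hypotheses (item 1) and again in the analysis plan (item 10), say "Should pre-treatment group differences be observed, differential improvements favoring the group hypothesized to improve would be observed" in that same baseline-adjusted comparison, and end: "No differences in this test indicate equivalence between interventions".

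Inference criteria sets p at .05 or lower and a Bayes factor of 3 or greater. It adds: "For the Bayes Factors, BF10 or BF01 will be reported based on which value is greater than 1 as recommended". It also says: "P-values will be considered primary in cases of discrepant results". Neither statement is tied to question 3. Sample size gives 27 children per group, and its rationale rests on recruitment dates and software readiness, with no power calculation or margin.

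**The concern.** A non-inferiority question needs a margin and a rule for ruling out differences larger than that margin. The plan has neither. A group-by-time test can show that two treatments differ, but failing to show it does not establish that CET is close enough to BPT.

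The equivalence sentence makes this worse for any outcome it covers, because it turns a non-significant result into a positive claim. In a small study, that claim would often be made when CET is in fact materially weaker than the treatment the plan itself calls the gold standard. If the sentence does not cover question 3, the answer would rest on a rule chosen after the results are known, which is what a preregistration is meant to prevent.

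**Working it through.** **1. Is there a decision rule?** The research question is non-inferiority, the hypothesis is improvement in both groups, and the critical test is a difference test. No section gives a margin, a confidence-interval criterion, two one-sided tests or a one-sided test. The stated sample size cannot be reproduced, because no power inputs are given.

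**2. Inputs for the size of the problem.** From the plan: 27 per arm and alpha .05. Assumed, because the plan does not give them: two-sided testing; pre-post correlation r = .5/.7/.8; between-subscale correlation .5; normal scores with SD 1 for a single subscale at each time. Effects are in that SD. Covariates and imputation are not modelled.

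**3. The plan's critical test.** Within a scale, group-by-time compares change averaged over the two subscales. The variance of one subscale's change is 2(1 − r). Averaging two, with correlation .5, gives 2(1 − r) × (1 + .5)/2 = 1.5(1 − r). So SE = √[(2/27) × 1.5(1 − r)], with 52 df and critical t = 2.007. The non-significance rates come from the noncentral t.

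| r | SE | 95% CI half-width | P(non-sig.), CET 0.5 SD worse | P(non-sig.), CET 0.3 SD worse |
|---|---|---|---|---|
| .5 | .236 | 0.47 | 45% | 76% |
| .7 | .183 | 0.37 | 23% | 64% |
| .8 | .149 | 0.30 | 9% | 49% |

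A result just short of significance has an interval reaching twice the half-width: a CET deficit of about 0.95/0.73/0.60 SD.

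**4. The test the equivalence sentence refers to.** For ANCOVA on one subscale, SE = √(2/27) × √(1 − r²) = .236/.194/.163, with 51 df. The non-significance rates are 45%/29%/15% for a 0.5 SD deficit and 76%/67%/56% for 0.3 SD.

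**5. Does the Bayes factor fill the gap?** I used the default two-sample Bayesian t-test with a Cauchy prior, as an approximation to the ANCOVA. With 27 per arm, BF01 at its maximum (t = 0) is 2.79, 3.65 or 4.91 for prior widths of 0.5, .707 or 1.0. The plan names no prior. At width 0.5 the threshold of 3 cannot be reached. At .707 it is reached only when |t| is at most 0.68, which happens in 50% of trials with no true difference. Even at |t| = 0.68 the ANCOVA interval reaches (0.68 + 2.008) × SE = 0.63/0.52/0.44 SD.

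**6. What would a margin test achieve?** For ANCOVA on the average of the two subscales, SE = √[(2/27) × .75(1 − r²)] = .204/.168/.141. With an illustrative margin of 0.5 SD, no true difference and one-sided .025, the noncentral t gives power of .67/.83/.93. Allowing for the small cost of estimating the baseline slope, it is about 67%/82%/93%.

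**The case against.** The strongest objection concerns scope. The equivalence sentence closes an item about interactions with a favoured group, and it follows a clause about baseline differences. For parent-rated ADHD symptoms no group is favoured, since both are expected to improve. On that reading the sentence does not govern question 3. This stands as a caution: a reader might infer that the plan commits to declaring CET equivalent to BPT on parent ratings whenever p exceeds .05, and the text does not settle that. But the test it names is the same ANCOVA that item 2 adopts as a post-hoc, so the reading is open. If it is rejected, question 3 is left with no rule at all.

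A reader might also infer that the plan never says how the subscales combine. It largely does. Group-by-time averages the two subscales within each scale, and the Measures section names the BASC-2 as the primary subjective assessment. Only a disagreement between BASC-2 and CSI-IV is unresolved.

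The reporting of BF01 gives some graded evidence about a null effect. That is to the plan's credit, but it tests a point null rather than a margin, depends on an unstated prior, and yields to the p-value when the two disagree.

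Finally, the expectation of no significant differences on the satisfaction and barriers scales might be taken as the same error. It states an expectation, not a reading of a null result.

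**Conclusion.** The point holds. Question 3 is posed as non-inferiority and analysed as difference, with no margin or interval rule. The equivalence sentence is invalid at 27 per arm for whatever outcomes it covers. On the plan's own critical test, a true 0.5 SD deficit would be missed in about 45%/23%/9% of trials and a 0.3 SD deficit in 76%/64%/49%. These figures depend strongly on the assumed correlations, and the documents do not say what deficit would matter clinically. They are rates of non-significance, not the probability that the trial will report equivalence: that would need a reporting rule the plan does not state.

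Parent-rated symptoms are a secondary outcome. A reader might infer that the main conclusion is at risk. It is not, because the primary working-memory hypothesis is one of superiority and its test is unaffected. This should be fixed, but it is not an obstacle to the study.

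**What to change.** Delete the equivalence sentence in both places (Recommended elements, items 1 and 10). Then choose one option before analysis.

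- **(a) Keep non-inferiority.** The co-PIs who have not seen the data set a margin in BASC-2 T-score points for the average of the two subscales. Non-inferiority is claimed only if the two-sided 95% confidence interval for the baseline-adjusted CET minus BPT difference excludes that margin. Otherwise the result is reported as inconclusive or, where the interval shows it, inferior.
- **(b) Drop the non-inferiority wording** from question 3 and report the adjusted difference with its 95% confidence interval.

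Under either option, state that question 3's between-group claim concerns parent ratings and that the actigraphy outcomes keep their superiority tests (Secondary Outcomes, items 3 and 4). Treat CSI-IV and BF01 as supportive, which also settles what happens if the two scales disagree. State that the comparison is sequential, not randomised and unblinded: a correct margin test would still be open to cohort and site differences.

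The cost is wording and one interval per outcome, with no new data. Option (b) is cheaper. The drawback of (a) is a real chance of an inconclusive answer: even with no true difference and an assumed margin of 0.5 SD, power is about 67%/82%/93%, and it would be lower for a tighter margin.
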